6.1.8 Duration of Therapy

All plugs will be inserted in to the lower punctum of the subject's schedule surgical eye 1 to 2 days prior to surgery and will remain in the study subject's lower punctum during cataract surgery and for a period of 2 weeks following surgery.

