2.3 Potential Risks and Benefits

2.3.1 Known Potential Risks

A study subject randomized to receive N-PPDS may have unforeseen risk and could exhibit moderate to severe post-op inflammation and/or ocular pain. However, the risk associated with using N-PPDS to deliver a sustain release of Nepafenac are anticipated to be similar, if not less than, those of commercially available topical 0.1% and 0.3% ophthalmic suspension

of Nepafenac and silicone punctal plug products. In ocular surgery clinical studies with Nevanac®, adverse reactions that occurred in 5-15% of study patients included capsular opacity, decreased visual acuity, foreign body sensation, increase intraocular pressure, and sticky sensation. Adverse reactions that occurred in 1-5% of study patients included conjunctival edema, corneal edema, dry eye, lid margin crusting, ocular discomfort, ocular hyperemia, ocular pain, ocular pruritus, photophobia, tearing and vitreous detachment. Some of these reactions may have been the consequence of the surgical procedure. A summary of known potential risks to humans of topical 0.1% and 0.3% ophthalmic suspension of Nepafenac can be found in the NEVANAC® and ILEVRO® prescribing information (see [Appendices 4 and 5](#)).

A study subject randomized to receive a placebo Punctal Plug Delivery System (p-PPDS) could exhibit moderate to severe post-op inflammation and/or ocular pain. Other risks associated with using a p-PPDS are anticipated to be similar to commercially available punctal plugs use in humans. A study subject could experience ocular discomfort, epiphora, loss of plug, ocular inflammation, and subconjunctival hemorrhage. Less common, but serious, side effects are pyogenic granuloma, damage to the muscle at the opening of the punctum, canaliculitis, or migration of the plug into the canaliculus requiring irrigation or surgery.

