6.1.7.2 Punctal Plug extruded pre-operative

If a study subject extrudes their plug prior to surgery, a new plug will be inserted in the lower punctum of the subject's scheduled surgical eye. The study subject will then be rescheduled for surgery in 1 to 2 days after re-insertion of the new plug. The punctal plug will remain in the study subject's lower punctum during cataract surgery and for a period of 2 weeks following surgery.

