7.4.5 Visit 7: (Final Study Visit, Day 14 ± 2 days Post-Op)

At the final scheduled study visit the following will be performed on the surgical eye only:

- a. Investigator evaluation of ocular pain

NOTE: The Investigator that interviewed and record the subject's response to ocular pain at Visit 4 (Day 1 post-op) should interview the subject at this visit

- b. Monocular Distance Visual Acuity (Uncorrected and Best-Corrected)
- c. Manifest Refraction
- d. Inspection of the masked punctal plug via the slit lamp
- e. Slit-Lamp examination

NOTE: The Investigator that performed slit-lamp evaluation at Visit 4 (Day 1 post-op) should perform the slit-lamp evaluation at this visit.

- f. Fundus examination
- g. Removal of the masked punctal plug
- h. Recording of any reported adverse event(s).
- i. Concomitant medication

An exit form will be completed at this final study examination (Visit 7), or whenever the study subject completes or leaves the study for any reason. The Investigator and/or his/her staff will review with each study subject the proper use or discontinuation of any post-op open-label medications prescribed by the Investigator. Any changes, discontinuation or addition of an open-label medication(s) must be recorded on the Concomitant Medication CRF.

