7.5 Emergency Anaphylactic or Overdose Procedures, Dose Modification

Dose modification of the study drug/device is not required in this study.

NOTE: Use caution when administering nepafenac to a subject who has previously exhibited sensitivities to phenylacetic acid derivatives and salicylate hypersensitivity as the potential for cross-sensitivity exists. This study is not expected to cause AEs different in type or intensity from those previously reported in published clinical research literature regarding the use of topical nepafenac (NEVANAC® or ILEVRO®). Refer to the Investigator Brochure and [Appendices 4 and 5](#) for additional information.

Should a subject experience a significant medical issue, the subject may be treated according to the Investigator's medical judgment. Any changes, discontinuation or addition of a post-op medication(s) must be recorded on the Concomitant Medication CRF.

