5.3 Corneal Effects

Use of topical NSAIDs may result in keratitis. In some susceptible patients, continued use of topical NSAIDs may result in epithelial breakdown, corneal thinning, corneal erosion, corneal ulceration or corneal perforation. These events may be sight threatening. Patients with evidence of corneal epithelial breakdown should immediately discontinue use of topical NSAIDs including NEVANAC® and should be closely monitored for corneal health.

Postmarketing experience with topical NSAIDs suggests that patients with complicated ocular surgeries, corneal denervation, corneal epithelial defects, diabetes mellitus, ocular surface diseases (e.g., dry eye syndrome),

Reference ID: 2966037

NDA 21-862/S-008
Page 6

rheumatoid arthritis, or repeat ocular surgeries within a short period of time may be at increased risk for corneal adverse events which may become sight threatening. Topical NSAIDs should be used with caution in these patients.

Postmarketing experience with topical NSAIDs also suggests that use more than 1 day prior to surgery or use beyond 14 days post surgery may increase patient risk and severity of corneal adverse events.

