5.3 Corneal Effects

Use of topical NSAIDs may result in keratitis. In some susceptible patients, continued use of topical NSAIDs may result in epithelial breakdown, corneal thinning, corneal erosion, corneal ulceration or corneal perforation. These events may be sight threatening. Patients with evidence of corneal epithelial breakdown should immediately discontinue use of topical NSAIDs including ILEVRO™ (nepafenac ophthalmic suspension), 0.3% and should be closely monitored for corneal health.

Postmarketing experience with topical NSAIDs suggests that patients with complicated ocular surgeries, corneal denervation, corneal epithelial defects, diabetes mellitus, ocular surface diseases (e.g., dry eye syndrome), rheumatoid arthritis, or repeat ocular surgeries within a short period of time may be at increased risk for corneal adverse events which may become sight threatening. Topical NSAIDs should be used with caution in these patients.

Postmarketing experience with topical NSAIDs also suggests that use more than 1 day prior to surgery or use beyond 14 days post-surgery may increase patient risk and severity of corneal adverse events.

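### The permitted plug schedule (up to 2 days pre-op, removal as late as Day 16) can pass both exposure thresholds in the appended nepafenac labels, and section 2.3.1 does not address this

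*Combined protocol and SAP*

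**What the plan says.** **Timing.** Section 6.1.8 places insertion "1 to 2 days prior to surgery and will remain in the study subject's lower punctum during cataract surgery" and adds two weeks of wear after surgery. The synopsis and sections 4.1 and 6.1.4 give the same insertion timing. Removal is a Visit 7 procedure, and section 7.4.5 titles that visit "Final Study Visit, Day 14 ± 2 days Post-Op"; Table 1 has the same window. For a plug lost before surgery, section 6.1.7.2 provides a replacement and adds: "The study subject will then be rescheduled for surgery in 1 to 2 days after re-insertion of the new plug".

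**Risk.** Section 2.3.1 says that the risks of delivering nepafenac through the plug "are anticipated to be similar, if not less than, those of commercially available topical 0.1% and 0.3% ophthalmic suspension" of nepafenac, and to those of silicone plugs. It lists some label reactions, corneal edema and dry eye among them, and refers to Appendices 4 and 5 for the rest.

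**Labels.** Section 5.3 of the 0.1% label (Appendix 4) gives this warning, drawn from postmarketing experience with topical NSAIDs: "use more than 1 day prior to surgery or use beyond 14 days post surgery may increase patient risk and severity of corneal adverse events". The 0.3% label (Appendix 5) gives the same two thresholds, ending "use beyond 14 days post-surgery may increase patient risk and severity of corneal adverse events". Both also state: "Patients with evidence of corneal epithelial breakdown should immediately discontinue use of topical NSAIDs".

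**Stopping.** Section 5.5.1.1 names ocular inflammation or pain of at least moderate degree, serious adverse events and death. Section 7.5 says: "Dose modification of the study drug/device is not required in this study".

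**The concern.** The protocol attaches the two labels as its source on nepafenac risk. Its own schedule allows exposure past both points at which those labels warn about the cornea, and the risk section neither repeats the warning nor explains why it would not carry over to the plug. An investigator, an IRB or a sponsor's safety reader working from section 2.3.1 alone would not learn that a fully compliant subject may fall in the range the labels describe.

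There is also an internal conflict that does not depend on the labels: two weeks of post-operative wear and a removal window reaching Day 16 cannot both describe the same maximum.

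Wear time will vary between subjects by several days. Section 10.4.4 plans no summary of exposure and section 10.4.5 marks adherence analyses as not applicable, so as planned the report would show corneal findings without the exposure behind them.

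**Working it through.** The plan gives no exposure figure to reproduce, so the check is day arithmetic on its stated windows.

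**Inputs.** Insertion 1 or 2 days pre-op (6.1.8). Removal on Day 12 to Day 16 (7.4.5: 14 - 2 to 14 + 2). Label thresholds 1 day before and 14 days after surgery (section 5.3 of Appendices 4 and 5).

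**Formulas.** Wear = insertion days + removal day. Pre-op excess = max(0, insertion days - 1). Post-op excess = max(0, removal day - 14).

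| Insertion | Removal | Wear (days) | Pre-op excess | Post-op excess |
|---|---|---|---|---|
| Day -1 | Day 12 | 13 | 0 | 0 |
| Day -1 | Day 14 | 15 | 0 | 0 |
| Day -1 | Day 16 | 17 | 0 | 2 |
| Day -2 | Day 12 | 14 | 1 | 0 |
| Day -2 | Day 14 | 16 | 1 | 0 |
| Day -2 | Day 16 | 18 | 1 | 2 |

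The two thresholds together span 1 + 14 = 15 days, so the permitted maximum of 18 is 3 days longer. In whole days there are 2 × 5 = 10 permitted combinations. Three pass neither threshold (Day -1 with Day 12, 13 or 14), three pass only the pre-op one, two only the post-op one, and two pass both. This counts what is allowed; the documents do not say how often each will occur.

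**Pre-op replacement (6.1.7.2).** Up to 2 days with the first plug plus up to 2 days after re-insertion gives 2 + 2 = 4 days from first insertion to surgery, less any time without a plug. This is the worst case: a Day -2 insertion, loss just before surgery, prompt replacement and the longer delay.

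**Could a lower drug load explain the risk sentence?** The insert holds 204 µg (6.1.2). The labels give 1 µg/µL and 3 µg/µL but no drop volume; I assume 25 to 50 µL. The labelled course covers 1 + 1 + 14 = 16 days.
- 0.1%: 3 × 16 = 48 drops, so 48 × 25 × 1 = 1,200 µg to 48 × 50 × 1 = 2,400 µg. The insert is 204/2,400 = 8.5% to 204/1,200 = 17% of this.
- 0.3%: 16 + 1 = 17 drops, so 17 × 25 × 3 = 1,275 µg to 17 × 50 × 3 = 2,550 µg. The insert is 204/2,550 = 8% to 204/1,275 = 16% of this.

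A lower total load is therefore plausible. The protocol gives no release rate, and section 2.3.1 does not make the argument.

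**What 50 active subjects can show.** The chance of seeing at least one event is 1 - (1 - p)^50: 39.5% at a true rate of 1% and 92.3% at 5%. With no events in 50, the one-sided 95% upper bound is 1 - 0.05^(1/50) = 5.8%. Any exposure table is descriptive.

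**The case against.** The strongest defence is that the central schedule is sound on its own terms. Two weeks matches the labelled duration, and Day -1 with removal by Day 14 stays inside both thresholds. The labels speak of what may happen with topical NSAIDs, and a small sustained-release insert may deliver less drug. Section 2.3.1 refers to the labels, and section 7.5 also points to an Investigator's Brochure that is not among the documents. All of this stands. It limits the point to the permitted extremes and rules out calling the risk sentence false. It does not reconcile the passages or supply the missing reasoning.

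A reader might infer several stronger things that the documents do not support:

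- *That investigator judgment is the only way to get the plug out.* The Medical Monitor may also end participation (5.5), 5.5.1.1 could cover a corneal event with marked inflammation or pain, need for an NSAID, steroid or immunosuppressant leads to removal (7.7.1), and every early exit includes removal (7.4.6). The statement on dose modification in 7.5 does not bar removal. What is true is narrower: corneal epithelial breakdown is not a named reason.
- *That the arms differ in exposure.* Both masked, randomised arms follow one schedule, and nothing suggests a systematic difference. The variation is between subjects.
- *That corneal findings cannot be related to exposure.* Insertion and removal dates are source data (11.1 g), and the cornea is graded at every post-operative visit. The analysis is simply not planned.
- *That the consent text is deficient.* It was not available to check.

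**Conclusion.** The point holds as a conflict between passages and an unexplained risk statement. A compliant site may keep a plug in for 13 to 18 days. At the extremes this is 1 day past the pre-op threshold (about 3 days, 4 - 1, counting from first insertion after a worst-case replacement) and 2 days past the post-op one. The Day 16 end also conflicts with the protocol's own two weeks. Section 2.3.1 neither mentions the corneal and duration warning nor says why it would not apply to a 204 µg insert.

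This rests on reading the visit window as the removal window, which 7.4.5 supports by listing removal as a Visit 7 procedure. It does not show that corneal risk is raised in this trial, and the number of subjects who would pass a threshold is unknown. About 50 are planned for active drug; because discontinued and disqualified subjects are replaced, the number exposed could be higher. The change should be made because it bears on subject safety and costs little. It does not call the randomised comparison into question.

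**What to change.** 1. Reconcile 6.1.8, 6.1.7.2, the Visit 2 timing and the Visit 7 removal window with each other and with section 5.3 of Appendices 4 and 5. The clinical team decides which governs.
2. Revise the risk sentence in 2.3.1 so that it either carries the labels' corneal and duration warning or states the basis, such as release data, for expecting similar or lower risk. Check that the consent risk text agrees. The same paragraph gives 5-15% for the commonest reactions where the appended labels give 5 to 10%, so check it against its source at the same time.
3. Reconcile 5.5.1.1 and 7.5 with the labels' text on corneal epithelial breakdown.
4. In 10.4.4, add a summary of days in situ by arm, from the dates already recorded under 11.1 g. List corneal findings against pre-op exposure and days in situ *when the finding was made*. Classifying subjects by eventual removal day would attach later exposure to findings from Visits 4 to 6.

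The cost is amendment wording, one descriptive table with a listing, and possibly tighter scheduling of Visit 2 or Visit 7, depending on how the passages are reconciled. No new data are needed.

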6.1.9 Removal of a Masked Punctal Plug

The masked punctal plug can be removed from the study subject's punctum using sterile ophthalmic forceps and a gentle tugging motion. A drop of anesthetic may be administered if necessary.

- a. Stabilize/constrain eyelid with fingers or with help from assistant
- b. It is recommended that a 0.12 1x2 teeth Castroviejo Suture forceps or similar toothed forceps with platforms should be used for plug removal. NOTE – using a jewelers forceps is not advisable
- c. Teeth should be placed on the far side of the plug with the blades straddling the neck
- d. Care must be taken not to grasp the outermost edge of the cap on the punctal plug as this may cause the cap to tear and separate, making it difficult to remove the plug from the canaliculus and/or causing plug intrusion.

- e. The teeth should not be used to grasp the plug but are used instead to prevent the blades of the forceps from sliding off the neck. Grasping the plug with the teeth may fracture it
- f. The motion to remove should be towards the medial canthus (not up or temporally), which is necessary to disengage the heel of the plug.

If the cap becomes separated, try to remove the plug using toothed 0.12 forceps (0.12 Castroviejo forceps or similar) by grasping the neck of the plug through the punctum. If this is not possible, and it doesn't seem as if the plug will lodge in the canal, and only if you feel comfortable doing so, you may attempt to irrigate the canal until the plug flushes out of the nasolacrimal duct.

NOTE: Study plugs are larger than commercially available silicone plugs and may become lodged in the canal more easily. Clinical judgment should be exercised when proceeding. Referral to tertiary care is advised in cases where the plug cannot be retrieved by massaging/milking through the punctal opening or by irrigation.

NOTE: Removal of a masked punctal plug immediately after insertion may result in the cap of the plug being torn off; the Investigator should wait at least 24 hours after insertion before attempting to remove a masked punctal plug. However, if the plug tears or separates, report this as a technical complaint. Retain the plug for accountability of investigational supplies.

6.2 Study Plug Accountability Procedures

The Investigator is responsible for maintaining the study treatment (punctal plugs) accountability log, which will contain inventory records acknowledging the receipt and dispensing of all study plugs. The study center will keep a complete accounting of all used, unused, damaged, extruded and lost study plugs. All lost/extruded study plugs must be recorded into the accountability log and on the CRFs of the study subject who lost/extruded their masked study plug, noting the suspected date the study plug was lost/extruded.

All used and unused masked study plugs must be accounted for and kept in the designated secure area at the study center until the Sponsor provides instructions for the return of all study materials. Final accountability for investigational study plugs will be verified by the Sponsor and/or their representatives and considered complete when the study plugs are no longer actively used and all study plugs (used, unused, extruded, lost) have been accounted for and returned to the Sponsor.

7 STUDY PROCEDURES AND SCHEDULE

Data will be captured and compiled using procedures developed by representatives of Mati Therapeutics Inc. All requested study data must be recorded clearly on study NCR CRFs and other study forms, as required. An explanation must be provided for all missing data. Only the Investigator or his/her staff members who are identified on the Study Personnel Identification List may enter or correct data on a CRF. Incomplete or inconsistent data on the CRFs will result in data queries that will require resolution by the Investigator.

7.1 Protocol Amendments

Modification of the protocol is prohibited without prior written agreement in the form of a protocol amendment. All amendments will be created by the Sponsor and must be approved by the IRB prior to implementation except when required to mitigate immediate safety risks or when the changes involve only logistical or administrative revisions.

7.2 Study Procedures/Evaluations

7.2.1 Study specific procedures

Procedures that will be required during the course of the study include (see [Section 7.4](#) for details):

- a. **Informed consent and HIPAA authorization:** The Investigator and or qualified staff will review and answer any questions a potential study subject may have regarding the study, the consent or HIPAA authorization forms. Prior to the initiation of any study specific activities, the subject must sign both documents
- b. Record subject's medical history for the previous 12 months and demographic data
- c. **Investigator evaluation of ocular pain:** The Investigator will interview and record subject responses in regards to any ocular pain they may be experiencing

NOTE: The Investigator that interviews and record subject responses to ocular pain at Visit 4 (Day 1 post-op) should interview the subject at ALL post-op visits (Day 3, 7, and 14).

- d. **Concomitant Medication use:** All prescription systemic, ophthalmic and over-the-counter concomitant medications used during the study, including all pre-, intra- and post-operative medications, including intravenous solutions, dilating drops, irrigations, viscoelastics, antimicrobials/anti-infective, miotics, etc. related to the surgery, will be documented. The medication name, start and stop dates, indication, dose, route of administration and any dosing alterations must be documented on the Concomitant Medications CRF through completion of the last study visit.
- e. **Distance Visual Acuity testing:** Visual acuity with and without correction, will be measured using a Snellen chart. The test distance and lighting conditions specified for the Investigator's chart must be used and kept constant throughout the study (see [Appendix 3](#) for details).
- f. **Manifest Refraction:** A phoropter or an auto refractor will be used to determine the study subject's best visual acuity with correction
- g. **Slit-Lamp Examination:** Slit-lamp examination will include assessment of the lid, conjunctiva, cornea and anterior chamber. Evaluation of the anterior chamber will be performed using a slit beam of 1 mm height and 1 mm width with maximum luminance

through the highest powered lens using the Investigator's standard slit lamp equipment and procedure. Grading of any slit lamp findings is defined in [Appendix 2](#).

NOTE: The investigator that performs the slit-lamp evaluation at Visit 4 (Day 1 post-op) should perform the slit-lamp evaluation at ALL post-op visits (Day 3, 7, and 14).

- h. Evaluation of lower punctum size
- i. Insertion of the study punctal plug, see [Section 6.1.6](#) of the protocol for details.
- j. Removal of the study punctal plug, see [Section 6.1.9](#) of the protocol for details.
- k. Fundus examination: The back part of the eye (fundus), including the retina, optic disc, choroid and blood vessels, will be examined using an ophthalmoscope (see [Appendix 3](#) for details)
- l. Adverse Event Reporting, see [Sections 8.3.1 and 8.3.2](#) of the protocol for details: To optimize consistency of AE reporting across centers, the study subject will be asked a standard question to elicit any AEs. At each study visit or telephone evaluation of the study subject, study personnel (non-observer) will ask the following question:

“Have you had any problems since your last visit?”

